**Signature Page**

## Revision History

Revision Number	Revision Date (DD/MMM/YYYY)	Reasons for Revision
V 1.0	13/JUN/2023	Original document: SAP template version 5.0 implemented.
V 2.0	07/NOV/2023	
1. Clarification was added on the definition of Esophageal Endoscopy (EE) analysis set in Section 5.0
 
2. Clarification was provided for different PVI Durability assessment scenarios in Section 7.1.4.
 
3. The analysis sets were modified to match what is specified in the CIP in Section 7.7.1
 
4. The site homogeneity analysis was removed due to not being proposed in CIP.
 
5. The details of operation definition of AAD failure (Day 105-Day 365) was provided. So AAD failure could be systematically evaluated in Section 7.3.4.3.
 
6. Acute procedural success was determined based on the targeted veins in which the entrance block could be determined, not on the clinical relevant PV anatomy in Section 7.3.2.

## List of Acronyms and Abbreviations

Acronym/ Abbreviation	Expanded Term
AAD	Antiarrhythmic Drug
AE	Adverse Event
AF	Atrial Fibrillation
AFEQT	Atrial Fibrillation Effect on Quality of Life
AFL	Atrial Flutter
AT	Atrial Tachycardia
CE	Conformite Europeenne
CEC	Clinical Events Committee
CRF	Case Report Form
CT	Cardiac Computed Tomography
CI	Confidence Interval
CIP	Clinical Investigation Plan
CSR	Clinical Study Report
DMC	Data Monitoring Committee
ECG	Electrocardiogram
EE	Esophageal Endoscopy
FU	Follow-Up
HM	Holter Monitoring
HRQoL	Health Related Quality of Life
LA	Left Atrial
LTE	Long-Term Effectiveness
mlITT	Modified Intent to Treat
MMSE	Mini Mental State Examination
MRA	Magnetic Resonance Angiogram
MRI	Magnetic Resonance Imaging
mRS	Modified Rankin Scale
NA	Neurological Assessment
NIHSS	National Institute of Health Stroke Scale
NSC	Non-Study Catheter
PAE	Primary Adverse Event
PAF	Paroxysmal Atrial Fibrillation
PEE	Primary Effectiveness Endpoint

Acronym/ Abbreviation	Expanded Term
PF energy	Pulsed Field Energy
PG	Performance Goal
PP	Per Protocol
PV	Pulmonary Vein
PVI	Pulmonary Vein Isolation
QoL	Quality of Life
RF	Radiofrequency
SADE	Serious Adverse Device Effect
SAE	Serious Adverse Event
SAP	Statistical Analysis Plan
SP	Safety Population
STSF	Thermocool Smarttouch Surroundflow
USADE	Unanticipated Serious Adverse Device Effect

## 1. Study Design

This clinical investigation is a prospective, single arm, multi-center and pre-market clinical evaluation of the Pulsed Field (PF)/Radiofrequency (RF) ablation system (THERMOCOOL SMARTTOUCH™ SF (STSF) Catheter and TRUPULSE™ Generator). The primary objective of this trial is to evaluate the safety and effectiveness of the system for the treatment of Paroxysmal Atrial Fibrillation (PAF).

The study will enroll 135 subjects who have drug refractory symptomatic PAF and are candidates for atrial fibrillation ablation. The study will be conducted at approximately 10 sites in Europe and potentially other regions. The primary safety endpoint is the occurrence of primary adverse events (PAEs) within 7 days of the index procedures, while the primary effectiveness endpoint is the electrical isolation of targeted PVs which will be evidenced by confirmation of entrance block. Both primary endpoints will be evaluated by using the 3-month follow-up data. The hypothesis testing of the primary endpoints will be performed when all subjects completed their 3-month follow-up. A clinical study report (hereinafter, 3-Month CSR) will be submitted as a part of the CE mark application dossier.

All subjects will be followed up for 12 months after their index ablation procedures and be assessed at 7 days, 1-, 3-, 6-, and 12-month scheduled follow-up visits. All study endpoints will be evaluated using the full 12-month follow-up data, except the hypothesis testing of primary endpoints. A clinical study report (hereinafter, Final CSR) will be compiled to present analysis results of all endpoints.

In addition to the main study, there will be four (4) subsets of subjects that will be embedded within the study. The first subset is the Neurological Assessment (NA) subset, which will assess the safety of the procedure in terms of neurological events or complications. The second subset is the Cardiac Computed Tomography (CT) or Magnetic Resonance Angiogram (MRA) image subset, which will assess the occurrence of PV stenosis. The third subset is the Esophageal Endoscopy (EE) subset, which will assess the presence of endoscopically detected thermal esophageal lesions (EDEL) in the region of the contact area between esophagus and LA. The fourth subset is the PVI durability subset, which will assess the durability of the lesion at 2-3 months after the index procedure. The same subjects are selected for all four (4) subsets.

## 2. Treatment Assignment

All subjects will be treated with the Biosense Webster PF/RF Ablation System, which includes the TRUPULSE™ Generator (D-1417-01-IC), the THERMOCOOL SMARTTOUCH™ SF (STSF) Catheter (D-1348-05-SI-10), and related components and accessories needed for the ablation procedure.

### 3. Randomization and Blinding Procedures

This is a non-randomized trial with all subjects receiving treatment with the PF/RF ablation system. Therefore, randomization and blinding of treatment assignments for operators and subjects will not be performed. To minimize operational bias, the study will maintain screening logs at each site to ensure that eligible subjects are considered for participation in the study.

### 4. Levels of Significance

The type-I error for testing each of the primary hypothesis tests is controlled at one-sided 2.5% level. The hypotheses of the primary endpoints will be tested at the full alpha level of 0.025, and only if it is success, the hypothesis testing of the secondary endpoint will be performed at the same alpha level. This gate-keeping approach will control the overall Type I error rate at one-sided 2.5%.

### 5. Analysis Sets

Analysis sets in this study are defined as the following:

- **Safety Population Analysis Set (SP):** The SP analysis set will include all enrolled subjects who have had the study catheter inserted, regardless of whether energy is delivered or not.
- **Modified Intention-To-Treat (mITT) Analysis Set:** The mITT analysis set will include enrolled subjects who meet the eligibility criteria and have had the study catheter inserted, regardless of whether energy is delivered or not.
- **Per Protocol (PP) Analysis Set:** the PP analysis set will only include enrolled eligible subjects who have undergone the ablation procedure using PF and/or RF energy via the investigational ablation system for the study-related arrhythmia. Subjects who have major protocol deviations that could affect the scientific integrity of the safety and effectiveness will be excluded from the PP analysis set, which includes (but not limited to):
  - Subjects who are found not to meet the eligibility criteria after undergoing the ablation procedure.
  - Subjects who fail in checking entrance block for each targeted PV after adenosine/isoproterenol challenge.
  - Subjects who undergo ablation using the investigational ablation system outside the PV/CTI region
  - Subjects who miss all CIP specified electrocardiographic effectiveness monitoring records.

- **Neurological Assessment (NA) Analysis Set:** The NA analysis set will include all NA subset subjects who have met the additional eligibility criteria specific for the NA subset and have had pre- and post-index-ablation procedure MRI and neurological assessments completed. Subjects who do not have a pre-index ablation procedure MRI assessment but have no lesions observed on post-procedure MRI assessment will still be included for analysis.
- **Esophageal Endoscopy (EE) Analysis Set:** The EE analysis set will include all EE subset subjects who have met the additional eligibility criteria specific for the EE subset and had a readable result of esophageal endoscopy assessment that is done within 1 to 3 days after the index-ablation procedure. Only subjects who have a readable esophageal endoscopy assessment within the specified time frame will be included in analyses for the EE endpoints.

*Note: Endoscopy preferable between 1 day to 3 days (72hours) post procedure. For procedures on Friday, a window of a maximum of 96 hours is justified.*

- **Cardiac CT/MRA Analysis Set:** The CT/MRA analysis set will include all CT/MRA subset subjects who have readable outcomes at both baseline and 3 months visit.
- **PVI Durability Analysis Set:** The PVI durability analysis set will include all durability subset subjects who have readable electro-anatomical mapping at the index ablation procedure and have the mapping 75 days (+/-15 days) post index ablation procedure.

Note that discontinued subjects are not subjected to the additional subset assessments (NA, EE, CT/MRA, and PVI durability).

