Cerebral ischemic lesions: An Asymptomatic Cerebral Emboli (ACE) is defined as an occlusion of a blood vessel in the brain due to an embolus that does not result in any acute clinical symptoms and is therefore 'silent'. Emboli can result from thrombus, gas, air, tissue, or fat. Source of micro-emboli include thrombi, which can develop on sheaths, materials, air introduction through sheath or during catheter exchange. Additionally, the hazard of microbubble formation in pulsed field ablation, leads to an unknown level of risk of ACE.⁴⁷ According to HRS guidelines, 2017, incidence of ACE is expected in 2%-15% as a complication to AF ablation.^{3, 38} However, literature on asymptomatic cerebral lesions after existing ablation modalities for AF (RF, Cryo) reports large variations between publications with rates that range from 2-40%.^{3, 48-55} Recent publications on detection of asymptomatic brain lesions when using PF energy for AF ablation show a similar trend and present rates from 3-40%.⁵⁶⁻⁵⁹ With either energy modality, the risk of ACE will be minimized by implementing an anti-coagulation regimen prior to catheter introduction into the LA and during procedure to avoid thrombi/emboli. To minimize the risk of air introduction, investigators will be trained on proper sheath handling, including removing air bubbles prior to insertion and will be instructed to minimize catheter exchange during the procedure.

Coronary Artery Spasm: Limited clinical data publications raised the potential for complication of coronary arterial spasm during ablation near the coronary arteries.^{32, 60, 61} Coronary artery spasm may lead to coronary artery stenosis/occlusion, heart attack (ventricular tachycardia) and or chest pain.^{3, 33, 60, 62} Energy application near the coronary arteries should be avoided to prevent coronary spasm. Per CIP, nitroglycerin (1-2mg) should be prepared when ablating near the coronary arteries. Administration of nitroglycerin, intravenous or intracoronary has been shown to be highly effective in attenuating the vasospasm.

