7.2 Study Subsets

7.2.1 Neurological Assessment (NA) subset

A focused neuropathological evaluation will be integrated within the study. This subset of subjects will represent the neurological assessment (NA) subgroup. Subjects will be assessed for incidences of post-ablation cerebral emboli with either an absence (asymptomatic) or presence (symptomatic) of neurological symptoms. Specifically, an asymptomatic cerebral embolism is defined as an occlusion of a blood vessel in the brain due to an embolus that does not result in any acute clinical symptoms. The presence (symptomatic) or absence (asymptomatic) of neurological symptoms will be determined by the site neurologist of the participating hospitals. The Cerebral MRI data will be analyzed by an independent Core Laboratory.

A total of 30 subjects will be prospectively included in this subset at sites with accessible MRI capabilities and a certified neurologist available to participate in the study. All subjects enrolled in the NA subset will meet all inclusion and exclusion criteria, including the additional exclusion criteria specific for the NA subset.

NA subset subjects will, in addition to the general follow-up schedule, undergo additional assessments including, Cerebral MRI, National Institute of Health Stroke Scale (NIHSS), Modified Rankin Scale (mRS), Mini Mental State Examination (MMSE) and general neurological assessments for evaluation of neurological incidences. NOTE: Patient questionnaires will only be used in countries with validated languages.

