7.3.4 Additional Safety Endpoints

Safety

- Incidence of Serious Adverse Device Effects (SADEs)
- Incidence of Unanticipated (Serious) Adverse Device Effects (UADEs and USADEs)
- Incidence of Serious Adverse Events (SAEs) within 7 days (early-onset), 8 to 30 days (peri-procedural) and >30 days (late onset) of index ablation procedure
- Incidence of non-serious adverse events (non-SAEs)

Neurological Assessment Subset

- Occurrence, anatomical location and size of new post-ablation asymptomatic and symptomatic cerebral emboli observed post-ablation as determined by Magnetic Resonance Imaging (MRI) evaluations
- Incidence of new or worsening neurological deficits post-ablation and at follow-up, compared to baseline
- Summary of Mini Mental State Examination (MMSE), National Institute of Health Stroke Scale (NIHSS) and Modified Rankin Scale (mRS) at baseline, post-ablation and during follow-up (if lesions were identified in prior evaluation)

CT/MRA Subset

- Occurrence of PV stenosis up to 3 months post-ablation as determined by Computed Tomography (CT)/ Magnetic Resonance Angiogram (MRA) evaluations.

Esophageal Endoscopy Subset

- Occurrence of endoscopically detected esophageal thermal lesions in the region of the contact area between esophagus and LA as determined by post procedure endoscopy.

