19.3 Analysis Sets

Safety Population Analysis Set (SP): The SP analysis set will consist of all enrolled subjects who have had insertion of the study catheter, regardless of energy delivery.

Modified Intention-To-Treat (mITT) Analysis Set: The mITT analysis set will consist of enrolled subjects who meet eligibility criteria and have had insertion of the study catheter.

Per Protocol (PP) Analysis Set: The PP analysis set will consist of subjects who satisfy the following criteria:

- Have undergone ablation using PF and/or RF energy via the investigational ablation system per CIP
- Are treated for the study-related arrhythmia
- Are enrolled and without major CIP deviation that would affect the scientific integrity of the safety and effectiveness, including but not limited to the following:
 - Subjects found not meeting eligibility criteria
 - Failure to check for entrance block for each targeted PV after adenosine/isoproterenol challenge.

- Use of the investigational ablation system outside the PV region. A CTI line for documented typical AFL identified prior to or during the procedure using investigational system or commercial RF devices to complete the procedure is allowed during index or repeat ablation procedure (within blanking). For the treatment of arrhythmia outside the PV region, using commercial RF devices to complete the procedure is allowed. However, subjects using commercial RF devices for the non-PV regions and/or CTI lines will be excluded from the 12-month effectiveness analysis.
- Missing all CIP specified electrocardiographic effectiveness monitoring

Neurological Assessment (NA) Analysis Set: The NA analysis set will include 30 subjects who have had pre-and post-index-ablation procedure MRI and neurological assessments completed. Subjects with no pre-index ablation procedure MRI assessment and no lesions observed on post-MRI assessment will be included for analysis.

Esophageal Endoscopy (EE) Analysis Set: The EE analysis set will include 30 subjects who have had a readable 1 to 3 days post index-ablation procedure esophageal endoscopy assessment.

Cardiac CT/MRA Analysis Set: The CT/MRA analysis set will include 30 subjects who have readable outcomes at baseline and 3 months.

PVI Durability Analysis Set: The PVI durability analysis set will include 30 subjects who have readable electro-anatomical mapping at index ablation procedure and 75 days (+/-15 days) post index ablation procedure.

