### 7.12.2 Analysis of NA Endpoint

The following analyses of neurological evaluations will be conducted and summarized descriptively. The analysis will be performed in the Neurological Analysis Set.

In addition to the criteria stated below, subjects will undergo full neurological follow-up only if neurologic symptoms and/or cerebral ischemic lesions are identified in a prior evaluation; results for these additional neurological evaluations will be summarized descriptively.

- **Neurological Exam:** The incidence of new or worsening neurological deficits post-ablation compared to pre-ablation will be summarized descriptively by timepoint.
- **Cerebral Emboli:** The frequency, anatomical location (side and area), and size (diameter and volume) of asymptomatic and symptomatic cerebral emboli observed pre-ablation and new emboli observed post-ablation as determined by MRI evaluations by the core lab will be summarized descriptively by timepoint.
- **Mini Mental State Examination (MMSE):** MMSE scores pre-ablation and change from pre-ablation at the 1-month follow-up will be summarized descriptively and plotted by timepoint.
- **National Institute of Health Stroke Scale (NIHSS):** NIHSS scores pre-ablation and post-ablation prior to discharge will be summarized descriptively and plotted by timepoint.
- **Modified Rankin Scale (mRS):** mRS scores pre-ablation and change from pre-ablation at the 1-month follow-up will be summarized descriptively and plotted by timepoint.

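### The neurological analysis set takes in subjects without a baseline MRI only when their post-procedure MRI is clean, which biases the new cerebral emboli rate downward

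*SAP*

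**What the plan says.** Under SAP section 5, NA subjects enter the analysis set if they meet the subset's eligibility criteria and "have had pre- and post-index-ablation procedure MRI and neurological assessments completed". The next sentence adds subjects that "do not have a pre-index ablation procedure MRI assessment but have no lesions observed on post-procedure MRI assessment will still be included for analysis". Protocol 19.3 carries the same exception: "Subjects with no pre-index ablation procedure MRI assessment and no lesions observed on post-MRI assessment will be included for analysis". Neither document admits a subject without a baseline MRI whose post-procedure MRI shows lesions.

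The set supports the endpoint in Protocol 7.3.4: "Occurrence, anatomical location and size of new post-ablation asymptomatic and symptomatic cerebral emboli observed post-ablation". SAP 7.12.2 summarises lesions seen before ablation and "new emboli observed post-ablation as determined by MRI evaluations by the core lab will be summarized descriptively by timepoint". On size, Protocol 7.2.1 states: "A total of 30 subjects will be prospectively included in this subset".

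**The concern.** Whether a subject without a baseline scan is counted depends on that subject's own result. A negative scan adds one event-free subject to the denominator. A positive scan removes the subject altogether. The exception can therefore add non-events only.

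The NA subset was set up to characterise symptomatic and silent emboli in a small group. Protocol 5.4.1 says the level of risk of asymptomatic cerebral emboli from microbubbles in pulsed field ablation is not known. Table 4 of the protocol excludes silent emboli from the primary adverse events, so the primary safety endpoint will not pick up what this set leaves out. Under SAP 7.12 the subset results go into the 3-Month CSR, which SAP 7.5 makes part of the CE mark dossier. Because SAP 7.12.2 uses the same set for the neurological exam, NIHSS, MMSE and mRS, the omitted subjects with lesions also leave those summaries.

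No planned analysis would reveal the effect. SAP 7.6 covers sensitivity analyses for the primary endpoints and SAP 7.10 those for the secondary endpoint; there is none for the NA endpoint.

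**Working it through.** The documents give no calculated figure for this endpoint, so there is nothing to reproduce. The check has two parts: the direction of the bias and its expected size.

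**Inputs**
- Subset size: 30 (Protocol 7.2.1).
- True rate of new lesions, p: Protocol 5.4.1 states that "incidence of ACE is expected in 2%-15% as a complication to AF ablation", and that pulsed field publications "show a similar trend and present rates from 3-40"%. I use 3%, 15% and 40% from these ranges, and 20% as an assumed intermediate value.
- Subjects without a baseline MRI, m: not given. Assumed 0 to 8, and missing for reasons unrelated to the outcome.
- Pre-existing lesions visible on the post-procedure scan: first assumed absent, then allowed for.

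**Direction.** Let n subjects have both scans, with x of them showing new lesions, and let k subjects have no baseline scan and a clean post-procedure scan.
- Rate in subjects with both scans: x/n.
- Rate under the plan's rule: x/(n + k).

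The second can never exceed the first, and is lower whenever x and k are both above zero. This needs no assumption about why scans are missing.

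**Size.** With n = 30 − m, the expected number of events is (30 − m)p and the expected number of clean subjects admitted without a baseline is m(1 − p). The reported rate is then about

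(30 − m)p / [(30 − m) + m(1 − p)].

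Examples:
- p = 20%, m = 3: 27 × 0.20 = 5.4 events; denominator 27 + 3 × 0.80 = 29.4; 5.4/29.4 = 18.4%.
- p = 40%, m = 3: 10.8/(27 + 1.8) = 10.8/28.8 = 37.5%.

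| True rate | m = 0 | m = 1 | m = 3 | m = 5 | m = 8 |
|---|---|---|---|---|---|
| 3% | 3.0% | 2.9% | 2.7% | 2.5% | 2.2% |
| 15% | 15.0% | 14.6% | 13.7% | 12.8% | 11.5% |
| 20% | 20.0% | 19.5% | 18.4% | 17.2% | 15.5% |
| 40% | 40.0% | 39.2% | 37.5% | 35.7% | 32.8% |

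The relative understatement is m(1 − p)/(30 − mp). At m = 1 it is 2% (p = 40%) to 3% (p = 3%); at m = 3, 6% to 10%. Averaging over the binomial distribution of k instead of using its expectation changes these figures by about 0.1 point at most (for example 35.8% instead of 35.7% at p = 40%, m = 5).

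If 20% of subjects have an old lesion visible on the post-procedure scan, fewer subjects without a baseline scan count as clean and the bias shrinks a little. At p = 15% and m = 6 the expected rate is 12.8%, against 12.4% with no old lesions. It is still downward.

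**Whole-number example.** Take 30 subjects, 5 without a baseline scan, and a true rate of 40%, so that 2 of those 5 have lesions and 3 are clean.
- Both scans required: 10/25 = 40.0%.
- Plan's rule: 10/(25 + 3) = 10/28 = 35.7%.
- Everyone with a post-procedure MRI, every undetermined lesion counted as new: 12/30 = 40.0%.

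**The case against.** The rule has a rationale. A clean post-procedure scan shows that there is no new lesion whatever the baseline looked like, whereas a positive scan without a baseline cannot separate new lesions from old. Each admitted subject is thus classified correctly. That is true but does not help: the bias comes from leaving out the comparable subjects with lesions, not from misclassifying those kept.

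The stronger objections concern size and consequence, and they stand as limits.
- The baseline MRI is mandatory within 72 hours before the procedure, or 96 hours for Monday procedures (Protocol 13.2.1), and a missed test is a deviation (Protocol section 16). The number missing may well be 0 to 2, in which case the shift is at most 40.0 − 38.4 = 1.6 points.
- With 30 subjects, the exact 95% interval is 7.7% to 38.6% for 6/30 and 22.7% to 59.4% for 12/30, so a shift of 1 to 2.5 points is small beside the sampling error. Imprecision does not excuse a bias of known direction, but it bears on priority.
- The endpoint is descriptive (Protocol 19.4.6), and no success criterion depends on it.
- Stroke, TIA and symptomatic thromboembolism are primary adverse events and are counted regardless of NA-set membership. A silent lesion reported as an adverse event would still appear in the general safety tables, though not in the NA rate.

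Finally, a downward bias against the true rate, as opposed to the rate in subjects with both scans, requires that baseline scans be missing independently of outcome.

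**Conclusion.** The concern holds. Both documents make entry to the NA set depend on the result being estimated, in one direction only. The CT/MRA set, by contrast, requires readable images at baseline and at 3 months with no exception for clean scans.

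Relative to subjects with both scans, the rule cannot raise the reported rate, and it lowers it whenever there are both events and clean subjects without a baseline. The size depends on an unknown count. There is no bias if every baseline scan is done. With 1 to 3 of 30 missing, the shift is at most 2.5 points over the rates considered, and with 8 missing it reaches 7.2 points at a true rate of 40%. These expected values assume that baseline scans are missing independently of outcome and that no old lesions are present.

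No hypothesis test or study success criterion is affected. The rule should still be corrected, because it understates a safety rate that will be reported for CE marking and no other planned analysis would show it.

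**What to change.** In Protocol 19.3 and SAP section 5, define the set for new emboli as subjects with both a pre- and a post-procedure MRI, whatever the post-procedure result, and delete the sentence that admits subjects without a baseline scan only when the later scan is clean. If baseline scans are missing independently of outcome, the expected rate then equals the true rate for any number missing.

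In SAP 7.12.2, add one sensitivity row that includes everyone with a post-procedure MRI and counts every lesion without a baseline scan as new. Label it an upper bound, since some of those lesions may be old. Report alongside it the number of subjects without a baseline MRI, split by post-procedure result.

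The cost is one sentence in each document and one table row, with no extra assessments. A few clean scans without a baseline leave the main denominator, but they remain in the sensitivity row.
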